Protocol Title: Metabolic, Hormonal, and Physiological Characterization of Isoenergetic High Intensity Interval Training and Moderate Intensity Continuous Training in Adults with Type I Diabetes

Principal Investigator: *[name]
Associate Professor
Director, Applied Physiology Laboratory
Department of Exercise & Sport Science
[name]
[contact]
Email: [contact]*

Co-Investigators: *[name]
Cary C. Boshamer Distinguished Professor of Nutrition & Medicine
Chair, Department of Nutrition*

*M. [name]
Medical Director, Diabetes Care Center Clinical Trials Unit
University of North Carolina*

*[name]
Resident Physician
Department of Family Medicine
University of North Carolina*

Funding Sponsor: *NC Diabetes Research Center
Bowman Gray Center for Medical Education
[name]
[name]*

Version Date: September 17, 2021

NCT Trial: **NCT04664205**

Study Summary

Title	Metabolic, Hormonal, and Physiological Characterization of Isoenergetic High Intensity Interval Training (HIIT) and Moderate Intensity Continuous Training (MICT) in Adults with Type I Diabetes (T1D)
Short Title	HIIT and T1D
Methodology	Randomized Controlled Cross-Over Design
Study Duration	Two years
Study Center(s)	Single site
Objectives	
Aim 1: To compare the metabolic responses immediately and 1 hr after one bout of HIIT compared to MICT matched for total energy expenditure, vs no exercise (control; CON) in 14 adults with T1D.
 
Aim 2: To evaluate key counter-regulatory/metabolic hormones during and after HIIT, MICT, and CON sessions and the change in glycemia (using continuous glucose monitoring and glycemic cutpoints [<70 mg/dL, 70-180 mg/dL, >180 mg/dL]) for 48 hrs post exercise.
 
Aim 3: To explore the modulatory effect of physiological variables on metabolism, including biological sex, lean body mass and visceral fat (measured from dual energy x-ray absorptiometry).

Number of Subjects	14 (7 females, 7 males)
Treatment Regimens	All subjects will undergo three conditions, in a randomized order: 
 1) HIIT 2) MICT 3) CON

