Specific Aim 1: To compare the metabolic responses immediately and 1 hr after HIIT compared to MICT matched for total energy expenditure, vs no exercise in 14 adults with T1D. Metabolism will be defined as energy expenditure (via indirect calorimetry), carbohydrate metabolism (tricarboxylic acid intermediates), and fat metabolism (acylcarnitines, respiratory exchange ratio).

Specific Aim 2: To evaluate key counter-regulatory/metabolic hormones (i.e. cortisol, lactate, glucagon, and insulin) during and after HIIT, MICT, and control (CON) sessions and the change in glycemia (using continuous glucose monitoring and glycemic cutpoints [<70 mg/dL, 70 - 180 mg/dL, >180 mg/dL]) for 48 hrs post exercise.

[figure not shown]
Specific Aim 3: To explore the modulatory effect of physiological variables on metabolism, including biological sex, lean body mass and visceral fat (measured from dual energy x-ray absorptiometry). Body fat percentage, lean mass, and visceral fat will be used to characterize the sample; the relationship of these variables with metabolomic intermediates will be assessed.

3 Study Design

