3.1 General Design

In a randomized controlled cross-over design, fourteen adults (7 females, 7 males) with T1D of at least 1-year duration and HbA1c $<9\%$ will undergo three conditions, in a randomized order: 1) high intensity interval training exercise session (HIIT) at 90% peak oxygen consumption (VO_2 peak); 2) moderate intensity exercise session (MICT; 65% VO_2 peak; or 3) a control session (CON; no exercise) (Figure 2).

Subjects will be asked to arrive to the laboratory after an overnight fast (8 hrs) and their usual dose of insulin administered the day prior, with no morning mealtime insulin the day of testing. The lower and higher limit for pre-exercise (i.e. fasted) glucose concentration (i.e. 10 minutes prior to the exercise start time) will be set at 90 and 250 mg/dL, respectively, and the session will be rescheduled if the pre-exercise glucose value is not in range or if hypoglycemia (blood glucose: <70 mg/dL) occurs within an hour of exercise start time. Subjects will also be asked to arrive to testing sessions following a 12 hour fast from caffeine and alcohol and to abstain from physical activity for 24 hours prior to testing. Subjects will complete one electronic contact (phone/email screening) and up to five in-person sessions (enrollment; baseline testing; three conditions [HIIT, MICT, CON]) over the course of 4 weeks

All data collection will be conducted by the Principal Investigator and Research Assistants. All subjects will report to the Applied Physiology Laboratory in [name] for consenting, enrollment, testing, and exercise sessions.

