Peak oxygen consumption (VO_2 peak; $L \cdot min^{-1}$ and $ml \cdot kg^{-1} \cdot min^{-1}$) will be used to set an appropriate individualized training load for the start of the HIIT protocol. During this ramp-based cycle ergometer test, respiratory gases will be analyzed over 15 second intervals using indirect calorimetry (Parvo Medics TrueMax 2400®, Salt Lake City, UT) until subjects reach volitional fatigue. The three highest oxygen consumption values will be averaged and recorded as the VO_2 peak. Ventilatory threshold (VT) will be determined as the intersection point of two linear regression lines fitted to the upper and lower portion of the ventilation versus VO_2 curve using manufacturer software (True One 2400® Metabolic Measurement System, Parvo-Medics Inc., Provo UT). Heart rate (HR) will be monitored throughout the test (Polar Electro Inc., Lake Success, NY), with the highest HR achieved during the test recorded as the HR_{max} . Interval intensity for the HIIT intervention will be calculated and set at 90% of the maximum wattage achieved. Intensity for the MICT intervention will be calculated and set at 65% of the maximum wattage achieved. Protocol was previously approved in IRB#16-2996, #16-0829, #14-2824, #14-0062 with no adverse events.

Familiarization and Randomization: (~10 minutes)

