Subjects will be familiarized with the cycle ergometer for the HIIT and MICT exercise. For familiarization, participants will practice a few intervals and cycle a few minutes at the individualized intensity for each respective exercise. They will also be asked, and provided with instructions, to practice one session (HIIT or MICT) on their own, under a usual fed state, prior to their visit to the lab. Each practice session will occur with CGM and Garmin physical activity monitoring (described below). The sessions should mimic those of the actual exercise session; 5-10 bouts of HIIT will be recommended; MICT time frame will be based on specific calculations (described below), approximately 15-25 min. This is included to provide the research team insight into potential glucose excursions prior to the lab-based exercise session in a fasted state. Our laboratory team has successfully implemented a similar 'home-based' HIIT intervention in healthy and clinical populations, with no adverse events [IRB: 18-2393 (Endometrial Cancer); 16-0829 (Knee osteoarthritis); 15-1150 (Bone marrow transplant patients); 14-2398 (Anterior Cruciate Ligament Reconstructive patients); 13-3515 (patients with cardiovascular disease risk factors)].

Visit 3-5: Randomized Treatment Regimen: (~90 minutes to 120 minutes)

At baseline testing, subjects will be randomized to one of three treatment regimens: 1) HIIT; 2) MICT; 3) CON (no exercise). Subjects will repeat the following procedures for visits 3-5, except there will be no exercise session on the CON treatment session. Exercise sessions will occur in the Applied Physiology Laboratory on the UNC campus. **There will be a minimum of seven days between each exercise trial.**

Continuous Glucose Monitoring (CGM):

Participants will be given the option to monitor their interstitial glucose levels via their own CGM or through a Freestyle Libre Pro (Abbot Laboratories), which will be provided to them. In the case that they decide to use their own CGM, the researchers will request data only for the dates the participant is involved in the study. If a participant decided to use the Freestyle Libre Pro, sensor will be inserted subcutaneously 7 days before exercise for a period of up to 7 days post exercise. CGM metrics including percent time-in-range (TIR), percent time in hypoglycemia, and percent time in hyperglycemia will be evaluated during and 48 hrs post exercise.

Dietary Controls:

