Approximately 8 mL of blood sample (~ 1.5 teaspoons) using an EDTA tube will be taken upon arrival, immediately after exercise, and one-hour post exercise. CON intervention visit will consist of a single blood draw. Circulating metabolites will be measured using an untargeted mass spectrometry-based platform with fasting concentrations of up to 1500 endogenous metabolites related to mitochondrial function, fatty acid oxidation, insulin resistance, and glucose regulation. Analysis will be completed at the Duke Molecular and Physiology Institute Metabolomics Core, directed by [name]. Targeted metabolomics analysis for acylcarnitines and amino acids will be completed; non-targeted analyses will also be performed, in order to promote the identification of unknown metabolites in addition to the known biology and physiology. Counterregulatory hormones (cortisol, lactate, glucagon) and insulin will be analyzed. Samples will be centrifuged immediately upon collection, and aliquots of plasma will be immediately frozen at -80° C for batch analysis. All blood draws will be done in the Applied Physiology Lab by an individual trained in phlebotomy. The current lab group has previously received approval for intravenous blood draws from the antecubital region in several IRB#, to name a few: 16-1991, 15-0543, and 14-0777, with no adverse events reported.

Treatment Regimens: (~20- 30 minutes)

- 1) HIIT Intervention: A 2 minute self-selected warm-up, followed by 10 alternating sets of one minute of pedaling at a resistance corresponding to 90% of VO₂peak and one-minute in active recovery at 50 watts (W). The work completed during each interval will be calculated by multiplying the power output for each participant at 90% VO₂peak by the duration of the interval (60 s). The work completed during each recovery period will be added by multiplying the power output (50 W) by the duration of the recovery period (60 s). The work from both bouts will be added together and then multiplied by 10 to calculate the total amount of work that each participant will complete in the HIIT trial.
- 2) MICT Intervention: Subjects will cycle continuously at a workload corresponding to 65% VO₂peak (W) for a pre-calculated length of time (~20-30 minutes), equivalent to the work that will be completed in the HIIT trials.
- 3) CON Intervention: No exercise will be performed. Subjects will arrive to the lab following the same pre-testing guidelines followed for HIIT and MICT trials.

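### HIIT and MICT loads are defined both as percent of VO2peak and as percent of maximum wattage, and the warm-up listed only for HIIT is left out of the work match

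*Combined protocol and SAP*

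**What the plan says.** **The claim of equality.** The title announces "Characterization of Isoenergetic High Intensity Interval Training and Moderate Intensity Continuous Training in Adults with Type I Diabetes". Specific Aim 1 in section 2 concerns "HIIT compared to MICT matched for total energy expenditure, vs no exercise in 14 adults with T1D". The paragraph that closes the Treatment Regimens text in section 4.1 repeats the claim of equal energy expenditure.

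**The loads, as percent of VO2peak.** Section 3.1 puts HIIT at 90% of VO2peak. Its MICT entry begins "moderate intensity exercise session (MICT; 65" and continues as a percentage of VO2peak. In the Treatment Regimens text HIIT is "A 2 minute self-selected warm-up, followed by 10 alternating sets of one minute of pedaling at a resistance corresponding to 90% of" VO2peak, with one-minute recoveries at 50 W. MICT there is at 65% of VO2peak, followed by (W).

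**The loads, as percent of wattage.** The Cardiorespiratory fitness text in section 4.1 opens by saying that VO2peak "will be used to set an appropriate individualized training load for the start of the HIIT protocol". It then states: "Interval intensity for the HIIT intervention will be calculated and set at 90% of the maximum wattage achieved", and "Intensity for the MICT intervention will be calculated and set at 65% of the maximum wattage achieved". No rule converts VO2 to watts, and nothing says which definition prevails.

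**The match.** HIIT work is ten times the sum of one 60-second interval and one 60-second recovery at 50 W. MICT lasts as long as it takes to do the same work, given as roughly 20-30 minutes. For the practice session, the Familiarization text says "MICT time frame will be based on specific calculations (described below), approximately 15-25 min". The 2-minute HIIT warm-up is not a term in the formula, and no MICT warm-up is listed.

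**The concern.** The trial isolates exercise intensity by holding the amount of exercise equal, so the plan has to fix two things without ambiguity: the intensity of each session and what is held equal.

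On intensity, percent of VO2peak and percent of maximum wattage agree only if oxygen uptake is proportional to power from zero. Cycling at zero watts still costs oxygen, so they do not agree. The gap is widest at lower intensities and therefore falls mainly on MICT, the session defined as moderate. Staff working from different parts of section 4.1 could set different watts and durations, and a report could state a dose that was not delivered.

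On equality, a warm-up that is listed for one session and not counted adds work to that session only. Because it is self-selected, the amount also varies between participants.

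**Working it through.** **Inputs from the protocol.** Fractions 0.90 and 0.65; recovery 50 W; ten pairs of one minute plus one minute; warm-up 2 min. **Assumed, because the protocol gives none of them:** peak ramp power W; oxygen uptake at zero watts as a fraction c of VO2peak, 0.10 to 0.25; warm-up power 25 to 75 W.

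**1. The plan's MICT duration.** With HIIT load aW and MICT load bW, equal work gives T = 10(aW + 50)/(bW) minutes. Under the wattage rule a = 0.90 and b = 0.65, so T = 13.85 + 769/W, with no physiological assumption.

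| Peak W | T, wattage rule (min) |
|---|---|
| 125 | 20.0 |
| 150 | 19.0 |
| 200 | 17.7 |
| 250 | 16.9 |
| 300 | 16.4 |

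Solving for W gives W = 500/(0.65T - 9). A time of 20 min needs 500/4 = 125 W, and 30 min needs 500/10.5 = 48 W. The practice-session range of 15-25 min corresponds to 500/0.75 = 667 W down to 500/7.25 = 69 W. Under the VO2peak rule (loads from step 2) T is 20.0-22.5 min at 150 W and 18.6-20.9 min at 200 W. The 20-30 min figure sits more easily with the VO2peak rule, and the 15-25 min figure is compatible with the wattage rule. The printed durations do not settle which is meant.

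**2. Difference in dose.** Assume VO2/VO2peak = c + (1 - c)P/W, where P is the power set.

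- 65% of maximum wattage: 0.10 + 0.90 × 0.65 = 0.685 of VO2peak; 0.25 + 0.75 × 0.65 = 0.738.
- 90% of maximum wattage: 0.10 + 0.90 × 0.90 = 0.910; 0.25 + 0.75 × 0.90 = 0.925.
- In reverse, 65% of VO2peak is (0.65 - c)/(1 - c) = 0.611 to 0.533 of maximum wattage, and 90% of VO2peak is 0.889 to 0.867.

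MICT shifts by about 4 to 9 percentage points of VO2peak, and HIIT by 1 to 2.5.

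**3. The uncounted warm-up.** Formula work is 10(aW + 50) watt-minutes.

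- Wattage rule: 10(135 + 50) = 1850 at 150 W; 10(180 + 50) = 2300 at 200 W.
- VO2peak rule with c = 0.25: 10(130 + 50) = 1800 at 150 W; 10(173.3 + 50) = 2233 at 200 W.
- Two minutes at 25, 50 or 75 W is 50, 100 or 150 watt-minutes.
- Smallest share: 50/2300 = 2.2%. Largest: 150/1800 = 8.3%. At 50 W the share is 100/2300 = 4.3% to 100/1800 = 5.6%.

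**4. Is equal work a fair proxy for equal energy?** In units of VO2peak-minutes, HIIT costs 20c + (1 - c)·Work/W and MICT costs Tc + (1 - c)·Work/W. Over peaks of 150-200 W, both rules and both values of c, the HIIT-minus-MICT gap without any warm-up runs from -4.3% (150 W, VO2peak rule, c = 0.25: 14.0 against 14.625) to +4.4% (200 W, wattage rule, c = 0.25: 13.625 against 13.048). With the same 50 W warm-up in both sessions it is -4.0% to +4.1%. This model covers aerobic energy during exercise only.

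**The case against.** The strongest defence is that there is really one rule. The fitness-test text is the only place that says how the loads are calculated. The MICT regimen carries (W) after its VO2peak percentage, and the HIIT work formula is written in power output. Percent of VO2peak then looks like loose shorthand for percent of peak watts. This largely stands: wattage is the likely working rule. It does not make the terms equivalent, and the sentence that opens the fitness-test text still credits VO2peak with setting the HIIT load.

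Second, no text forbids a MICT warm-up; it is only unlisted. That is fair, and the imbalance therefore holds for the plan as written. If both sessions share a warm-up in practice, it disappears.

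Third, describing sessions matched for external work as isoenergetic is mainly a matter of terminology. The formula is explicit, and step 4 supports work as a reasonable proxy.

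Some stronger inferences should be resisted:

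- *That the printed durations prove the VO2peak rule.* The 20-minute figure is approximate, and the wattage rule gives 19.0 min at 150 W. The same 20-30 minute range heads the regimens as a whole, so it may be a session slot. With a 2-minute MICT warm-up, that slot would reach 20 min at any peak up to 500/(0.65 × 18 - 9) = 185 W.
- *That the energy gap is +1% to +13%.* The model does return that range when a 25-75 W warm-up is added to HIIT only. The upper end stacks a 200 W peak, a 25% intercept, the wattage rule and a 75 W warm-up, none of which is in the protocol. About 4 points of it are present with no warm-up at all.
- *That the calorimetry fails as a check on the match.* The protocol uses the first and last three minutes to describe caloric expenditure and fuel use. It does not present them as verification of the match.

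**Conclusion.** The point holds as an inconsistency in the stated dose and an omission from the work match. It does not invalidate the comparison. A reader might infer that two load definitions bias HIIT against MICT. The documents do not support that: both loads come from one ramp test per participant, and the formula equates the work of the ten pairs with MICT under either rule, so a rule applied consistently leaves the within-participant contrast intact. What would be wrong is the label. MICT reported at 65% of VO2peak would be nearer 69-74% if wattage was used, given an intercept of 10-25% of peak uptake and a linear relation that ignores the lag of VO2 behind power in a ramp test.

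The warm-up, as written, puts HIIT work above MICT work for any load above zero: about 2-8% of formula work under the assumed warm-up powers and peaks. The direction follows from the text, provided that MICT has no unlisted warm-up; the size rests on the assumptions. Both points should be corrected, because intensity and equality define the comparison and the correction is cheap.

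**What to change.** - State one intensity rule in section 3.1, the fitness-test text and the Treatment Regimens text. The simplest is 90% and 65% of the maximum wattage reached in the ramp test.
- If percent of VO2peak is kept instead, give the conversion to watts and correct it for the lag of VO2 behind power. A plain regression of ramp-test VO2 on watts would overstate the steady load for 65% of VO2peak.
- Give both sessions the same 2-minute warm-up at a fixed load, for example 50 W, the existing recovery load. Alternatively, add the warm-up work to the formula; at 50 W and a 200 W peak under the wattage rule this lengthens MICT by 100/130 = 0.8 min. The load must then be fixed in advance, because the order is randomised and MICT time may have to be set before the HIIT session takes place.
- Restate the expected MICT duration. Under the wattage rule it is about 16-20 min for peaks of 125-300 W, excluding warm-up.
- Define isoenergetic once, as matched for external work.

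The cost is wording and about two extra minutes in the MICT session. Gas exchange throughout both sessions would allow a direct statement about energy expenditure, but it is optional and not needed for this correction.

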Statistical Methodology	
Aim 1: Principal Component Analysis for metabolomics data; two-way ANOVA [regimen (HIIT vs. MICT vs. CON) \times time (base vs. immediate post vs. 1h post)]
 
Aim 2: Two-way mixed-factorial ANOVA for counterregulatory hormones; Comparison of area under the curve across all trials for CGM, aggregated over 24 hrs
 
Aim 3: Spearman correlations between metabolomic outcome and physiological variables)

Abbreviations and Definition of Terms

Abbreviations and Definitions of Terms	
Abbreviation:	Formal Title:
HIIT	High Intensity Interval Training
MICT	Moderate Intensity Continuous Training
T1D	Type 1 Diabetes
CON	Control (no exercise)
CGM	Continuous Glucose Monitoring
HbA1c	Hemoglobin A1c
VO ₂ peak	Peak Oxygen Consumption
PAR-Q+	Physical Activity Readiness Questionnaire
BMI	Body Mass Index
4C Model	Four Compartment Model
FM	Fat Mass
%fat	Percent Body Fat
LM	Lean Mass
DXA	Dual-energy x-ray Absorptiometry Total Body Scan
BIS	Bioelectrical Impedance Spectroscopy
VT	Ventilatory Threshold
HR	Heart Rate
HR _{max}	Maximal Heart Rate
TIR	Time-in-Range
CHO	Carbohydrate
PRO	Protein
FAT	Fat
NDSR	Nutrient Data System for Research
ELISA	Enzyme-Linked Immunosorbent Assay
MVPA	Moderate-Vigorous Physical Activity
EDTA	Ethylenediaminetetraacetic acid
W	Watts
EXSS-IRB SOP	Exercise and Sport Science Institutional Review Board Standard Operating Procedures
DAIDS	Division of AIDS
AE/SAE	Adverse Event/Serious Adverse Event
UPIRSO	Unanticipated Problems Involving Risks to Subjects or Others
DSMB	Data and Safety Monitoring Board
APL	Applied Physiology Laboratory

1 Introduction

This document is a protocol for a human research study. This study will be conducted according to US and international standards of Good Clinical Practice (FDA Title 21 part 312 and International Conference on Harmonization guidelines), applicable government regulations and Institutional research policies and procedures.

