3.2 Primary Study Outcomes

The primary study outcomes include circulating metabolites that will be measured using an untargeted mass spectrometry-based platform with fasting concentrations of up to 1500 endogenous metabolites related to mitochondrial function, fatty acid oxidation, insulin resistance, and glucose regulation. Targeted metabolomics analysis for acylcarnitines and amino acids will be completed; non-targeted analyses will also be performed as an exploratory analysis, in order to promote the identification of unknown metabolites in addition to the known biology and physiology. Responses will be collected prior to, immediately post, and 1 hr post exercise.

3.2a. Secondary Study Outcomes

Counterregulatory hormones (cortisol, lactate, glucagon) will be evaluated at the same time points. Glucose will be continuously monitored for 48 h post exercise. , and glycemic control through 48 hrs after HIIT, compared to MICT versus a no exercise CON.

3.2b. Tertiary Study Outcomes

Tertiary outcomes will evaluate the influence of biological sex and physiological outcomes (i.e. body composition, lean mass, visceral fat) on the metabolomics profile of these subjects.

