5.2 Statistical Methods

For aim 1, changes in the first principal component, as well as any additional components for which the associated eigenvalue is greater than one, will be evaluated using paired t-tests at the 2-sided 0.05 level. Changes in individual metabolic intermediates will be evaluated using paired t-tests at the 2-sided 0.01 level. Differences in metabolomics and counterregulatory hormones markers between treatment regimens will be evaluated using two-way ANOVAs [regimen (HIIT vs. MICT vs. CON) \times time (base vs. immediate post vs. 1h post)]. Exploratory analysis of the modulatory effects of sex on metabolomics markers will be evaluated using separate regimen-by-sex mixed factorial ANOVAs [regimen \times sex], at each time point.

For aim 2, CGM data will be evaluated as previously recommended; data will be aggregated over the 24hrs; area under the curve data will be compared across trials.(25) Counter-regulatory hormones will be evaluated using a two-way mixed factorial ANOVA. Activity data will be captured to potentially be used as a covariate when collating CGM data.

For aim 3, spearman correlations will be completed to understand associations between metabolomics outcomes and physiological variables (i.e. body fat, lean mass, visceral fat).

6 Safety and Adverse Events

Risks associated with participating in this study are **possible**. In-test monitoring by the research team, who are certified fitness professionals trained in CPR/AED, are in place to ensure the safety of all subjects. Personnel trained in phlebotomy and with radiation exposure training will complete the blood draws and DXA scans, respectively.

In accordance with the Exercise and Sport Science Institutional Review Board Standard Operating Procedures (EXSS-IRB SOP), 3 trained research personnel (for safety purposes per IRB procedures) will perform cardiorespiratory fitness testing. Other precautions include: licensed medical professional (MD, ATC) on call, operational AED, and a land line within 10 feet of the testing in order to make emergency call, if required. Additionally, the lab is located within 500 feet of the University Athletic Training facility. If a cardiovascular event does occur, 911 will be called; UNC Hospitals and Emergency room are in very close proximity to the lab.

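### Section 4.1 gives the control visit one blood draw, so the planned 3 x 3 regimen-by-time ANOVA cannot be run as specified and change from baseline versus CON cannot be estimated

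*Combined protocol and SAP*

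**What the plan says.** **Sampling.** Section 4.1 (Metabolomics) sets blood draws on arrival, straight after exercise and an hour later. It then says: "CON intervention visit will consist of a single blood draw". No time is given for that draw. Earlier in Section 4.1, under Visit 3-5, the plan says: "Subjects will repeat the following procedures for visits 3-5, except there will be no exercise session on the CON treatment session". Read alone, that implies the full sampling schedule at CON.

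**Analysis.** Section 5.2 says that metabolomic and hormone markers "will be evaluated using two-way ANOVAs [regimen (HIIT vs. MICT vs. CON", crossed with time at base, immediate post and 1 h post. The Study Summary gives the same model for Aim 1: "two-way ANOVA [regimen (HIIT vs. MICT vs. CON", by the same three times. Section 5.2 also plans "separate regimen-by-sex mixed factorial ANOVAs" at each time point.

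**Aims.** In Section 2, Aim 1 is to "compare the metabolic responses immediately and 1 hr after HIIT compared to MICT matched for total energy expenditure, vs no exercise". Aim 2 covers hormones "during and after HIIT, MICT, and control (CON) sessions". Section 3.2a adds: "Counterregulatory hormones (cortisol, lactate, glucagon) will be evaluated at the same time points". These are the three times given for the primary metabolite outcome in Section 3.2.

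**The concern.** The sampling schedule and the analysis describe different data sets. A regimen-by-time ANOVA with CON as a level needs a CON value at each time, and the schedule provides one.

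The purpose of the control visit is at stake. Participants arrive fasted, and metabolites and hormones may move over the morning without any exercise. Only repeated CON samples can separate that drift from the response to exercise. Drift common to both exercise visits cancels in HIIT versus MICT, so the loss is confined to comparisons with CON. Those comparisons are nevertheless an explicit part of Aim 1, which concerns the primary outcome, and of the hormone part of Aim 2. Samples that are not drawn cannot be recovered later.

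**Working it through.** The plan gives no count of cells or samples to reproduce. The argument is structural and does not depend on the effect size, correlation or N = 12 in Section 5.1.

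**Inputs.**
- HIIT and MICT: 3 draws each (Section 4.1).
- CON: 1 draw, time not stated (Section 4.1).
- ANOVA: 3 regimens x 3 times (Section 5.2, Study Summary).
- Enrolment: 14 (Section 5.1).

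**Cells and samples.**
- Cells needed per participant: 3 x 3 = 9. Cells observed: 3 + 3 + 1 = 7. Cells empty: 2.
- Samples needed with 14 completers: 14 x 9 = 126. Collected: 14 x 7 = 98. Short: 28.
- With 12 completers: 108 needed, 84 collected, 24 short.
- The same two cells are empty for everyone, so there are 0 complete cases.

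**Could another sample fill the gap?** No blood draw is described at baseline testing. Calorimetry is tied to the start and end of the exercise bout. Neither supplies the missing CON values.

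**Contrasts with CON.** Let μ(r,t) be the mean for regimen r at time t (0 = base, 1 = immediate post, 2 = 1 h post). A contrast is estimable only if every cell it uses is observed.
- Change from baseline versus CON is [μ(HIIT,t) − μ(HIIT,0)] − [μ(CON,t) − μ(CON,0)] for t = 1, 2, and likewise for MICT. That makes four contrasts. Each needs two CON cells, and only one exists.
- Time-matched level versus CON is μ(HIIT,t) − μ(CON,t) for t = 1, 2, and likewise for MICT. That makes four more contrasts. Each needs the CON cell at that time.

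| Time of the single CON draw | Change versus CON | Post-exercise level versus CON | HIIT − MICT levels | HIIT − MICT changes |
|---|---|---|---|---|
| Arrival | 0 of 4 | 0 of 4 | 3 of 3 | 2 of 2 |
| Immediate post | 0 of 4 | 2 of 4 | 3 of 3 | 2 of 2 |
| 1 h post | 0 of 4 | 2 of 4 | 3 of 3 | 2 of 2 |

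**Interaction.** The planned degrees of freedom are (3 − 1)(3 − 1) = 4. Seven observed cells give rank 7. The additive model uses 1 + 2 + 2 = 5, which leaves 7 − 5 = 2. Both come from HIIT versus MICT, where (2 − 1)(3 − 1) = 2. The HIIT-versus-CON main effect, averaged over three times, is also lost because it needs all three CON cells.

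**Trial fit with 14 simulated participants.** A standard repeated-measures ANOVA rejected the seven-cell layout as unbalanced. With nine cells it ran with interaction df 4 and 52. With HIIT and MICT only, it ran with df 2 and 26.

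**Sex analyses.** A regimen-by-sex ANOVA at each time has CON data at only one of the three times.

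**The case against.** - **The single draw is a deliberate exception.** Section 4.1 defines the later draws relative to exercise, and a specific statement normally overrides a general one. On that reading the two parts of Section 4.1 agree. This is fair, but it removes only that conflict. The conflict with Section 2, Section 5.2 and the Study Summary remains. It also makes arrival the natural time for the draw, which is the case with no time-matched post-exercise contrast.
- **A mixed model could use seven cells.** It could be fitted, but the plan names an ANOVA. Any change versus CON would then rest on CON values staying constant over a fasted visit. The plan does not state that assumption, and one sample cannot test it.
- **Much survives.** This stands. HIIT versus MICT is intact, and it is the contrast that supplied the effect sizes in Section 5.1. The paired t-tests of change still run within HIIT and within MICT. The CGM comparisons with CON are untouched, and a post-exercise value can still be set against the one CON value, though not at a matched time. The affected sex analyses are labelled exploratory.
- **Two side points.** No draw is planned during exercise in any regimen, so that part of Aim 2 is not specific to CON. Section 5.2 does name regimen and time for hormones in its Aim 1 paragraph. Its Aim 2 paragraph then calls the hormone model mixed factorial without giving factors, although regimen and time are both within-subject. That is a minor matter of wording.

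**Conclusion.** The concern holds. With one CON draw, 2 of 9 cells are empty for every participant and the 3 x 3 ANOVA cannot be run as specified for metabolites or hormones. No change-from-baseline contrast with CON is estimable, whatever the draw time. At most 2 of 4 time-matched post-exercise contrasts with CON are estimable, and none if the draw is at arrival. The only assumption is that the single-draw statement means what it says. The sample counts further assume that all 14 participants complete. This must be fixed because it concerns a stated comparison on the primary outcome, but the damage does not reach HIIT versus MICT.

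**What to change.** Reconcile the Study Summary and Sections 2, 3.2, 3.2a, 4.1 and 5.2, and state the number and timing of CON draws. Two routes are open.

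**(a) Sample CON fully.** Draw at arrival, after a rest matched to the exercise time, and one hour later. The 3 x 3 within-subject analysis can then stay. The cost is two more 8 mL draws per participant (16 mL) and 14 x 2 = 28 more samples to assay. Section 4.1 already allots about 90 to 120 minutes to each of visits 3-5, CON included.

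**(b) Keep the single draw.**
- State its time.
- Restate the metabolite and hormone analysis as 2 regimens (HIIT, MICT) x 3 times, with CON as a resting reference only.
- Limit the regimen-by-sex ANOVAs to HIIT and MICT at times with no CON sample.
- Remove the post-exercise claim against no exercise for blood markers from Aims 1 and 2. If a comparison with the one CON value is kept, label it as not time-matched and state the assumption that CON is constant over the visit.

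This costs wording only. Its downside is a narrower claim, with no properly controlled comparison of post-exercise blood markers. It is the only route for participants whose CON visit has already taken place with one draw.

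Under either route, name the factors of the hormone ANOVA in the Aim 2 paragraph. If regimen and time are the only two, drop the word *mixed*.
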